# 6.0 Complaints

A Complaint is any written, electronic, or oral communication that alleges deficiencies related to the physical characteristics, identity, quality, purity, potency, durability, reliability, safety, effectiveness, or performance of a product/device after it is released for distribution.

Complaints associated with any component of this investigational product must be reported to the Sponsor (Section 6.2.2). For adverse events, please refer to Section 6.1 through Section 6.1.6. For product complaints, please refer to Section 6.2.

All adverse events will be followed to a satisfactory conclusion.

# 6.1 Medical Complaints

The investigator will monitor each subject for clinical and laboratory evidence of adverse events on a routine basis throughout the study. The investigator will assess and record any adverse event in detail including the date of onset, event diagnosis (if known) or sign/symptom, severity, time course (end date, ongoing, intermittent), relationship of the adverse event to study drug, and any action(s) taken. For serious adverse events considered as having "no reasonable possibility" of being associated with study drug, the investigator will provide an Other cause of the event. For adverse events to be considered intermittent, the events must be of similar nature and severity. Adverse events, whether in response to a query, observed by site staff, or reported spontaneously by the subject will be recorded.

All adverse events will be followed to a satisfactory conclusion.

#### 6.1.1 Definitions

#### 6.1.1.1 Adverse Event

An adverse event (AE) is defined as any untoward medical occurrence in a patient or clinical investigation subject administered a pharmaceutical product and which does not necessarily have a causal relationship with this treatment. An adverse event can therefore be any unfavorable and unintended sign (including an abnormal laboratory finding), symptom, or disease temporally associated with the use of a medicinal (investigational) product, whether or not the event is considered causally related to the use of the product.

Such an event can result from use of the drug as stipulated in the protocol or labeling, as well as from accidental or intentional overdose, drug abuse, or drug withdrawal. Any worsening of a pre-existing condition or illness is considered an adverse event. Worsening in severity of a reported adverse event should be reported as a new adverse event. Laboratory abnormalities and changes in vital signs are considered to be adverse events only if they result in discontinuation from the study, necessitate therapeutic medical intervention, and/or if the investigator considers them to be adverse events.

A BMD decrease at any anatomic location (lumber spine, total hip or femoral neck) during the Treatment Period that leads to discontinuation from study drug should be reported as an adverse event.

An elective surgery/procedure scheduled to occur during a study will not be considered an adverse event if the surgery/procedure is being performed for a pre-existing condition and the surgery/procedure has been pre planned prior to study entry. However, if the pre-existing condition deteriorates unexpectedly during the study (e.g., surgery performed earlier than planned), then the deterioration of the condition for which the elective surgery/procedure is being done will be considered an adverse event.

#### 6.1.1.2 Serious Adverse Events

If an adverse event meets any of the following criteria, it is to be reported to AbbVie as a serious adverse event (SAE) within 24 hours of the site being made aware of the serious adverse event.

**Life-Threatening** An event that, in the opinion of the investigator, would

have resulted in immediate fatality if medical intervention had not been taken. This does not include an event that would have been fatal if it had occurred in a more severe

form.

Hospitalization or Prolongation of Hospitalization An event that results in an admission to the hospital for any length of time or prolongs the subject's hospital stay.

This does not include an emergency room visit or

admission to an outpatient facility.

**Congenital Anomaly** An anomaly detected at or after birth, or any anomaly that

results in fetal loss.

Persistent or Significant Disability/Incapacity

An event that results in a condition that substantially interferes with the activities of daily living of a study subject. Disability is not intended to include experiences of relatively minor medical significance such as headache, nausea, vomiting, diarrhea, influenza, and accidental

trauma (e.g., sprained ankle).

Important Medical
Event Requiring
Medical or Surgical
Intervention to Prevent
Serious Outcome

An important medical event that may not be immediately life-threatening or result in death or hospitalization, but based on medical judgment may jeopardize the subject and may require medical or surgical intervention to prevent any of the outcomes listed above (i.e., death of subject, life-threatening, hospitalization, prolongation of hospitalization, congenital anomaly, or persistent or significant disability/incapacity). Additionally, any elective or spontaneous abortion or stillbirth is considered an important medical event. Examples of such events include allergic bronchospasm requiring intensive treatment in an emergency room or at home, blood dyscrasias or convulsions that do not result in inpatient hospitalization, or the development of drug dependency or drug abuse.

[figure not shown]
For serious adverse events with the outcome of death, the date and cause of death will be recorded on the appropriate case report form.

## 6.1.1.3 Adverse Events of Special Interest

For some adverse events, such as SAEs and adverse events of special interest (AESI), such as elevated liver transaminases, bone mineral density decrease/fractures, and mood and depression-related events, hot flashes and other non-bone hypoestrogenic events, lipid abnormalities, cardiovascular events, thromboembolic events, hormonally sensitive malignancies, and alopecia, AbbVie may require additional information, including family history, to be collected and recorded in the eCRF.

#### 6.1.2 Adverse Event Severity

The investigator will use the following definitions to rate the severity of each adverse event:

Mild The adverse event is transient and easily tolerated by the subject.

**Moderate** The adverse event causes the subject discomfort and interrupts the

subject's usual activities.

**Severe** The adverse event causes considerable interference with the

subject's usual activities and may be incapacitating or life

threatening.

## 6.1.3 Relationship to Study Drug

The investigator will use the following definitions to assess the relationship of the adverse event to the use of study drug:

**Reasonable** After consideration of factors including timing of the event, biologic plausibility, clinical judgment, and potential alternative

causes, there is **sufficient** evidence (information) to suggest a

causal relationship.

No Reasonable After consideration of factors including timing of the event,

Possibility biologic plausibility, clinical judgment, and potential alternative

causes, there is **insufficient** evidence (information) to suggest a

causal relationship

For causality assessments, events assessed as having a reasonable possibility of being related to the study drug will be considered "associated." Events assessed as having no reasonable possibility of being related to study drug will be considered "not associated." In addition, when the investigator has not reported a causality or deemed it not assessable, AbbVie will consider the event associated.

If an investigator's opinion of no reasonable possibility of being related to study drug is given, an Other cause of event must be provided by the Investigator for the serious adverse event.

#### 6.1.4 Adverse Event Collection Period

All adverse events reported from the time of study drug administration until 30 days following discontinuation of study drug administration have elapsed will be collected, whether solicited or spontaneously reported by the subject. All nonserious adverse events of bone fracture, clinically significant BMD loss, or newly diagnosed medically-related bone condition will be collected during the Post-Treatment Follow-Up Period, until the subject discontinues from study participation. In addition, serious adverse events and protocol-related nonserious adverse events will be collected from the time the subject signed the study-specific informed consent.

Adverse event information will be collected as shown in Figure 4.

[figure not shown]
[figure not shown]

Figure 4. Adverse Event Collection

#### **COVID-19 Pandemic-Related Acceptable Protocol Modifications**

Supplemental study case report forms should be completed in the event of COVID-19 related missed/virtual visits, study drug interruptions or discontinuations, or adverse events (including capture of specific signs/symptoms of infection and testing results).

COVID-19 infections should be captured as adverse events. If the event meets the criteria for a serious adverse event (SAE), then follow the SAE reporting directions per the protocol and above. The following COVID-19 related supplemental eCRFs should be completed:

- COVID-19 Supplemental Signs/Symptoms
- COVID-19 Status Form
   If a subject has a confirmed or suspected COVID-19 infection and study drug was interrupted, the Investigator should contact the Sponsor emergency

medical contact listed above before reintroducing study drug.

## 6.1.6 Pregnancy

Pregnancy in a study subject must be reported to AbbVie within 1 working day of the site becoming aware of the pregnancy. Subjects who become pregnant during the Treatment or Post-Treatment Follow-Up Periods of the study must be discontinued (Section 5.4 and Section 5.4.1). A positive urine pregnancy test result must be confirmed with a serum pregnancy test. While waiting for the results of the serum pregnancy test, study drug should be temporarily discontinued pending results of the serum pregnancy test. If a serum pregnancy test result is positive at any time during the Treatment Period of the study, the site will immediately inform the subject to discontinue study drug. However, an ultrasound examination will be performed as early as possible during the first trimester of pregnancy to assess the gestational age and document an intrauterine pregnancy. Information regarding a pregnancy occurrence in a study subject and the outcome of the

pregnancy will be collected for any study subject with a positive serum pregnancy test after receiving at least one dose of study drug through 30 days following the last dose of study drug. The site will report a positive pregnancy test to the Sponsor, will follow the course of the subject's pregnancy, and report to the Sponsor on the health of the subject and fetus at each trimester, the newborn at the first post-delivery pediatrician visit and the infant 6-12 months post-delivery.

If the subject has a positive serum pregnancy test during the Treatment or Post-Treatment Follow-Up Periods of the study, no additional study procedures, including protocol required DXA scans, will be conducted. The following information on the outcome of the pregnancy should be collected: fetal outcome (e.g., spontaneous or elective abortion, live infant or still birth), date and mode of delivery, birth weight, birth length, gender, any congenital anomaly and medically significant complications during pregnancy or labor or delivery. For live infant births, information on the health of the infant will be collected from the first post-delivery pediatrician visit and at 6 to 12 months after delivery.

For each subject with a confirmed pregnancy, the Investigator will provide information about the option to participate in an elagolix pregnancy registry (P18-954) for pregnancy outcomes. The contact information for the Bloom Pregnancy Registry is in the Oriahnn/Orilissa label (pregnancy registry [contact]).

Pregnancy in a study subject is not considered an adverse event. However, the medical outcome for mother or infant, meeting any serious criteria including an elective or spontaneous abortion, stillbirth or congenital anomaly is considered a serious adverse event and must be reported to AbbVie within 24 hours of the site becoming aware of the event.

### 6.2 Product Complaint

#### 6.2.1 Definition

A Product Complaint is any Complaint (see Section 6.0 for the definition) related to the biologic or drug component of the product.

For a product this may include, but is not limited to, damaged/broken product or packaging, product appearance whose color/markings do not match the labeling, labeling discrepancies/inadequacies in the labeling/instructions (example: printing illegible), missing components/product, or packaging issues.

Any information available to help in the determination of causality by the product to the events outlined directly above should be captured.

#### 6.2.2 Reporting

Product Complaints concerning the investigational product must be reported to the Sponsor within 24 hours of the study site's knowledge of the event via the Product Complaint form. Product Complaints occurring during the study will be followed-up to a satisfactory conclusion. All follow-up information is to be reported to the Sponsor (or an authorized representative) and documented in source as required by the Sponsor. Product Complaints associated with adverse events will be reported in the study summary. All other complaints will be monitored on an ongoing basis.

[figure not shown]
Product Complaints may require return of the product with the alleged complaint condition (investigational product). In instances where a return is requested, every effort should be made by the investigator to return the product within 30 days. If returns cannot be accommodated within 30 days, the site will need to provide justification and an estimated date of return.

The description of the complaint is important for AbbVie in order to enable AbbVie to investigate and determine if any corrective actions are required.

#### 7.0 Protocol Deviations

AbbVie does not allow intentional/prospective deviations from the protocol unless when necessary to eliminate an immediate hazard to study subjects. The principal investigator is responsible for complying with all protocol requirements, and applicable global and local laws regarding protocol deviations. If a protocol deviation occurs (or is identified,

including those that may be due to the COVID-19 pandemic), the principal investigator is responsible for notifying Independent Ethics Committee (IEC)/Independent Review Board (IRB) regulatory authorities (as applicable), and their assigned Clinical Monitor or the following AbbVie Clinical Study Team members:

Such contact must be made as soon as possible to permit a review by AbbVie to determine the impact of the deviation on the subject and/or the study.

# 8.0 Statistical Methods and Determination of Sample Size

## 8.1 Statistical and Analytical Plans

Complete and specific details of the statistical analysis will be described and fully documented in the Statistical Analysis Plan (SAP).

#### 8.1.1 General Considerations

The SAS system will be used to perform the statistical analyses. All statistical tests will be two-sided and a significance level of 0.050 will be used unless otherwise specified. A test will be deemed statistically significant if the P value rounded to three decimal places is less than or equal to 0.05 unless otherwise specified.

In general, data will be summarized for the 12-month placebo-controlled double-blind Treatment Period, the open-label Treatment Period, and the Post-Treatment Follow-Up Period separately.

In the 12-month placebo-controlled double-blind Treatment Period, data will be summarized by treatment group (the elagolix 300 mg BID plus E2/NETA group and the placebo group). Comparisons of safety will be made between the elagolix 300 mg BID plus E2/NETA group and the placebo group in the 12-month Treatment Period.

In the open-label Treatment Period, summaries will be provided for each of the following treatment groups of subjects.

- 1. Subjects randomized to elagolix 300 mg BID plus E2/NETA in the 12-month Treatment Period and continued to receive elagolix 300 mg BID plus E2/NETA in the open-label Treatment Period;
- 2. Subjects randomized to placebo in the 12-month Treatment Period, and switched to elagolix 300 mg BID plus E2/NETA in the Open-label Treatment Period.

Statistical tests will only be made in the double-blind Treatment Period. No statistical tests will be made in the Open-label Treatment Period and the Post-Treatment Follow-Up Period.

## 8.1.2 Data Sets Analyzed

#### **Full Analysis Set**

The full analysis set which is comprised of all randomized subjects who took at least one dose of the study drug will be used for all efficacy analyses and baseline analyses unless otherwise specified in the Statistical Analysis Plan (SAP). The data from the full analysis set will be presented by the treatment group assigned at the time of randomization.

#### Safety Analysis Set

The safety analysis set includes all randomized subjects who took at least one dose of the study drug. Subjects will be analyzed according to the treatment they actually received, defined as the randomized treatment if the patient took at least one dose of that treatment during the 12-month placebo-controlled double-blind Treatment Period, or the first treatment received if the randomized treatment was never received during the 12-month placebo-controlled double-blind Treatment Period. All safety analyses will be performed based on the safety analysis set unless otherwise specified in the SAP.

The All Elagolix plus E2/NETA Analysis Set is defined as subjects who received at least 1 dose of elagolix plus E2/NETA in the study (either in the placebo-controlled or openlabel Treatment Periods). Subjects will be summarized based on the actual treatment received at the time of randomization (elagolix plus E2/NETA or placebo).

# 8.1.3 End of 12-Month Placebo-Controlled Treatment Period Analysis

An end-of-placebo-controlled treatment period analysis will be performed after the last subject completes the 12-Month placebo-controlled Treatment Period. These analyses will include data collected during the Treatment Period (placebo-controlled and openlabel Treatment Periods) and the Follow-Up Period up to the data cut-off for the interim lock. The database will be versioned for an interim lock and any discrepant data will be clarified before the versioning. Analyses will be performed by AbbVie.

Since this end-of-placebo-controlled treatment period analysis is the only and final analysis for the comparison between treatment and placebo group at 12 months of safety and efficacy endpoints, no additional adjustment of alpha-level is necessary.

## 8.1.4 Treatment Month 24, Month 36, Month 48 and Other Timepoints Analyses

At the end of Treatment Month 24, Month 36, Month 48 or other timepoints during the open-label period, analysis of the safety and efficacy safety variables may be performed

after the last subject completes the Treatment Month 24, Month 36, Month 48 visit or other timepoint during the open-label period, respectively. For subjects who prematurely discontinued during the treatment period, their data collected during the Follow-up Period will be included in the analysis, as appropriate. The database will be versioned for an interim lock and any discrepant data will be clarified before the versioning. Analyses will be performed by AbbVie.

## 8.1.5 Demographic, Baseline Characteristics and Concomitant Medications

Demographic and baseline characteristics will be summarized by treatment group.

Medical history and gynecological medical/surgical history data will be coded using system organ classes (SOCs) and preferred terms (PTs) from the Medical Dictionary for Regulatory Activities (MedDRA) by treatment group. The duration of the study drug exposure will be summarized by treatment group.

Protocol deviations and reasons for discontinuation will be summarized.

Concomitant medications will be coded using the World Health Organization (WHO) dictionary and summarized with frequencies and percentages.

Unless noted otherwise, the baseline values will be defined as the last non-missing assessment obtained prior to the initiation of the study drug unless otherwise specified.

#### 8.1.6 Efficacy

## 8.1.6.1 Primary Efficacy Variable

### 8.1.6.1.1 Primary Analysis

As the objective of this study is to evaluate the long-term safety and tolerability of elagolix 300 mg BID with E2/NETA, no primary or secondary efficacy endpoint is defined.

## 8.1.6.2 Other Efficacy Variables

Other assessments during the placebo-controlled double-bind 12-month Treatment Period include the following:

- PGIC for Menstrual Bleeding Symptom;
- Change from baseline for the UFS-QoL.

#### **UFS-QoL**

Improvement in quality of life will be assessed on the UFS-QoL Questionnaire (4-week recall). The change from baseline to each scheduled assessment will be calculated and summarized for each of the UFS-QoL subscales (symptom severity, concern, activities, energy/mood, control, self-conscious and sexual function) and the Health Related Quality of Life Questionnaire (HRQoL) total. The change from Baseline to Month 6 and Month 12 during the double-blind Treatment Period will be analyzed using ANCOVA with treatment as the main effect and corresponding Baseline UFS-QoL as a covariate to compare the elagolix dose group to placebo.

#### **PGIC for Menstrual Bleeding (PGIC-MB):**

PGIC-MB is to assess the change in subjects' severity of menstrual bleeding. The number and percentage of subjects in each response category based on PGIC-MB will be summarized at Month 3, Month 6, Month 9 and Month 12 by treatment group. The number and percentage of subjects with response of (a) "Very Much Improved" or "Much Improved," and (b) "Otherwise" will be summarized by treatment group in the 12-month Treatment Period. Comparisons will be made using a Miettinen–Nurminen (M-N) test.

#### 8.1.7 **Safety**

#### 8.1.7.1 General Considerations

All randomized subjects who took at least one dose of the study drug will be included in the safety analyses.

For continuous variables, descriptive statistics (mean, standard deviation, median, minimum and maximum) will be summarized by treatment group. The treatment group differences in change and percent change from baseline will be analyzed using a one-way ANOVA with treatment as the main effect in the 12-month Treatment Period unless otherwise specified in the SAP.

Categorical data will be summarized with frequencies and percentages by treatment group. Chi-square test or Fisher's exact test (or its generalization to  $r \times c$  tables) will be used to analyze treatment group differences for qualitative categorical variables in the 12-month Treatment Period unless otherwise specified in the SAP.

Missing safety data will not be imputed.

Analysis details will be specified in the SAP.

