#### **Statistical Methods (Continued):**

#### Safety:

All randomized subjects who took at least one dose of the study drug will be included in the safety analyses. The number and percentage of subjects having adverse events will be tabulated by primary SOC and MedDRA Preferred Term with a breakdown by treatment group. Hematology, lipid panel, vital signs, endometrial safety via TVU/TAU and endometrial biopsy, and pregnancy results will be summarized.

For continuous variables, descriptive statistics (mean, standard deviation, median, minimum, and maximum) will be summarized by treatment group. The treatment group differences in change and percentage change from baseline will generally be analyzed using a 1-way analysis of variance (ANOVA) with treatment as the main effect in the 12-month Treatment Period, unless otherwise specified.

Categorical data will be summarized with frequencies and percentages by treatment group. Chi-square test or Fisher's exact test will be used to analyze treatment group differences for qualitative categorical variables as appropriate in the 12-month Treatment Period, unless otherwise specified.

The within-group percent change from baseline to Months 6, 12, 18, 24, 30, 36, 42 and 48 in BMD will be summarized for each treatment group. The percent change from baseline to Month 6 and Month 12 in BMD will be compared between the elagolix 300 mg BID plus E2/NETA group and the placebo group.

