## 8.2 Determination of Sample Size

Approximately 500 subjects will be randomized (2:1) to elagolix 300 mg BID plus E2/NETA (N = 335) and placebo (N = 165).

Based on clinical review, a sample size of 500 was selected to gather long term safety exposure data in approximately 50 subjects completing 48 months of study drug dosing, with approximately 30 subjects receiving 48 months of active drug elagolix 300 mg BID plus E2/NETA 1/0.5 mg QD.

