# TEAEs during the open-label Treatment Period on the Safety Analysis Set during the open-label Treatment Period

TEAEs during the open-label Treatment Period are defined as any AEs with the onset that is on or after the first dose of study drug during the open-label Treatment Period and no

more than 30 days after the last dose of study drug in the study. AEs starting more than 30 days following discontinuation of study drug will not be included in summaries of treatment-emergent AEs but will be summarized separately.

TEAEs for All Elagolix plus E2/NETA Analysis Set

TEAEs for All Elagolix plus E2/NETA Analysis Set are defined as any AEs with the onset that is on or after the first dose of elagolix plus E2/NETA (either in the placebocontrolled Treatment Period or open-label Treatment Period) and no more than 30 days after last dose of elagolix plus E2/NETA. AEs starting more than 30 days following discontinuation of study drug will not be included in summaries of treatment-emergent AEs but will be summarized separately.

The number and percentage of subjects experiencing treatment-emergent AEs will be summarized overall, as well as by primary MedDRA SOC and PT by treatment group. The SOCs will be presented in alphabetical order, and the PTs will be presented in alphabetical order within each SOC.

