## 9.5.4 Endometrial Biopsy

For the Safety Analysis Set, the number and percentage of subjects in each category of endometrial biopsy results will be summarized by treatment group at each relevant visit during the placebo-controlled and open-label Treatment Periods. If multiple assessments existed in a specific time window, all assessments will be displayed.

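### Year 1 binary harms are compared with placebo without a risk difference, confidence interval or upper bound

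*Protocol*

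**What the plan says.** The first objective (Protocol 4.0, SAP 2.1) is to assess safety against placebo at 12 months.

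For categorical safety data, Protocol 8.1.7.1 names a chi-square or Fisher test that "will be used to analyze treatment group differences for qualitative categorical variables in the 12-month Treatment Period unless otherwise specified in the SAP". The synopsis says the same: "Chi-square test or Fisher's exact test will be used to analyze treatment group differences for qualitative categorical variables". Protocol 8.1.1 sets the threshold: "All statistical tests will be two-sided and a significance level of 0.050 will be used unless otherwise specified", with significance when the "P value rounded to three decimal places is less than or equal to 0.05".

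The sections on particular harms are descriptive. For treatment-emergent events, SAP 9.2.1 says "The number and percentage of subjects experiencing treatment-emergent AEs will be" tabulated overall and by MedDRA term. SAP 9.2.2, 9.2.5 and 9.2.6 do likewise for SAEs, discontinuations and AESIs, with listings under 9.2.5. SAP 9.5.3.1 gives counts and percentages for ovarian cysts. For biopsies, SAP 9.5.4 says "the number and percentage of subjects in each category of endometrial biopsy results will be summarized by treatment group". Protocol 8.1.7.2, 8.1.7.5 and 8.1.7.6 also stop at numbers and percentages for these outcomes. Rates per 100 patient-years (SAP 9.2.4) cover only the All Elagolix set, with no placebo comparison and no interval.

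Between-group 95% intervals are planned for percent change in BMD (Protocol 8.1.7.4), selected laboratory variables (SAP 9.3) and vital signs (SAP 9.4).

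**The concern.** SAEs, thromboembolic and cardiovascular events, fractures, hepatic events and endometrial pathology are the outcomes for which a trial of this size says least through a P value. They are also the outcomes for which the plan offers no estimate of the difference and no statement of its uncertainty.

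The gap exists on either reading of the documents. If the Protocol default applies to adverse events, the comparison is a P value with little chance of being significant for a rare harm. If the SAP's silence means that adverse events are described only, the comparison is two percentages side by side. In neither case does the report state the largest excess risk that the data leave open.

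**Working it through.** **Inputs.** Arm sizes are 335 and 165 (Protocol 8.2); the SAP (2.4) has 333 and 167. Alpha is two-sided 0.05, with P rounded to three decimals (Protocol 8.1.1). The sample size was chosen by clinical review, and no event rate, power or detectable difference is stated, so there is no planned figure to reproduce. Counts below are women with at least one event, out of all randomised.

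**Step 1: P values for 7 against 0 at 335:165.**
- Fisher: given 7 events in all, the hypergeometric probability that all 7 fall on elagolix is 0.05935. The tables no more probable than this have 2, 1 or 0 of the 7 on elagolix (0.03609, 0.00576, 0.00039). The sum is P = 0.1016.
- Pearson chi-square: 500 × (7 × 165)² / (335 × 165 × 7 × 493) = 3.497, so P = 0.0615.

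| Women with event | Fisher P | Chi-square P |
|---|---|---|
| 7 v 0 | 0.102 | 0.061 |
| 8 v 0 | 0.057 | 0.045 |
| 9 v 0 | 0.034 | 0.034 |

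At the SAP's 333:167, 7 against 0 gives 0.101 and 0.059. So 7 against 0 is the largest split against zero that is non-significant under both tests. At 8 against 0 the answer depends on which test is used, and the documents give no rule for choosing.

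**Step 2: how often the test would miss.** The true risks here are assumptions shown as a range. As context only, Protocol 3.2.2 reports treatment-emergent SAEs in 1.3% to 6.5% of women per group in Cohort 2 of the Phase 2b study. For 2% against 0%, significance needs at least 9 events (Fisher) or 8 (chi-square) among 335 women. The binomial probabilities are 0.231 and 0.356, so the miss rates are 77% and 64%. Exact enumeration, counting only rejections in the direction of harm, gives:

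| Assumed true risk | Miss rate, Fisher | Miss rate, chi-square |
|---|---|---|
| 1% v 0% | 99% | 98% |
| 2% v 0% | 77% | 64% |
| 3% v 1% | 80% | 74% |
| 5% v 2% | 69% | 64% |

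If only about three quarters of the women had an evaluable result (250 v 124, an assumption relevant to scans and biopsies), the miss rates for 2% against 0% would be 93% and 87%.

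**Step 3: what an interval would show.** The Miettinen-Nurminen limits are the differences d at which (observed difference − d) / √V = ±1.96. Here V is the variance at the restricted maximum-likelihood estimates, multiplied by N/(N−1) = 500/499. With no placebo events the restricted placebo risk at the upper limit is 0, so the upper limit solves (observed − d)² = k·d(1 − d), with k = 1.96² × (500/499) / 335 = 0.01149.
- 0 v 0: d = k/(1 + k) = 0.0114, an upper limit of +1.1 points.
- 7 v 0: observed 7/335 = 0.0209. At d = 0.0425 both sides equal 0.000468, so the upper limit is +4.3 points. The lower limit, found numerically, is −0.2 points.
- 3 v 0: −1.4 to +2.6 points.
- 8 v 0: +0.1 to +4.6 points.

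To one decimal, the 7 v 0 interval is the same at 333:167.

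**Step 4: the uncontrolled period.** For zero events in n women, the exact two-sided 95% upper limit is 1 − 0.025^(1/n). This is 7.1% for the roughly 50 planned 48-month completers and 11.6% for the roughly 30 with 48 months of active drug (Protocol 8.2).

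**The case against.** A reader might infer that rare harms are judged only by a P value, so that 7 against 0 would be declared no significant difference. The documents do not support that as fact. The test is a default that yields to the SAP, and the SAP names a categorical safety test only for the BMD and endometrial-thickness bands. Its adverse event, cyst and biopsy sections contain no test and no P value. Read as purely descriptive, the plan would print 7 (2.1%) against 0 (0%). However, SAP 9.1 rules out testing only for the open-label period and the All Elagolix set. The Protocol default for Year 1 is therefore not withdrawn either.

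A reader might also infer that P above 0.05 will be taken as safety. No passage says so: Protocol 8.1.1 defines significance, not a safety conclusion. Rare harms are also assessed through relatedness, severity, subject listings, AESI searches and hepatic threshold counts.

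Three further points are fair. The interval can be derived from the tabulated counts, so no information is lost. The interval for 7 against 0 includes zero, so a reader looking only for significance learns nothing new from it. And the sample size was chosen for long-term exposure, so low power for rare harms contradicts no stated aim.

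These points limit the finding to one of reporting. They do not supply the missing measure of uncertainty, and a reader should not have to compute it.

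**Conclusion.** The point holds as a gap in reporting. For Year 1 binary harms, the comparison named in the first objective carries no risk difference, interval or bound, whether or not the Protocol's default test applies. The size of the gap is shown by 7 against 0: not significant by either test (P = 0.10 or 0.06), yet compatible with an excess of up to 4.3 per 100 women. No events in either arm leaves up to 1.1 per 100 open. These figures assume the planned arm sizes with every woman counted. The miss rates also rest on assumed event risks, because the plan gives none.

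No planned estimate is biased or invalidated. The change is worth making because it is cheap and because the plan already reports uncertainty this way for its continuous safety measures.

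**What to change.** - **SAP 9.2.2, 9.2.5, 9.2.6 and 9.5.3.1:** for the placebo-controlled period, add the elagolix-minus-placebo risk difference with a two-sided Miettinen-Nurminen 95% interval. Apply it to any SAE, any AE leading to discontinuation, each AESI group and the pre-defined ovarian cysts. These are added columns; there is no P value in those sections to replace. SAP 8.5.1 already uses the related Miettinen-Nurminen test for PGIC-MB, but only its P value, so the interval must be specified.
- **Protocol 8.1.7.1:** state that for these outcomes the interval is the basis of the comparison and that P above 0.05 is not evidence of no harm. This also settles how the Protocol default and the SAP's silence fit together.
- **SAP 9.5.4:** add the same interval for endometrial hyperplasia or worse, with the denominator stated: all dosed women and, separately, those biopsied. Both are needed because the Month 12 biopsy depends on endometrial thickness measured after randomisation.
- **Optional:** give exact Clopper-Pearson 95% limits for the Month 24 to 48 biopsy proportions, which have no control.

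The cost is wording and a few table columns, with no new data, visits or patients. The downside is that the report will show visibly wide intervals for rare events.
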